Scientific Protocol

**Transnasal Humidified Rapid-Insufflation Ventilatory Exchange (THRIVE) Use in
Pediatric Populations**

Scientific Protocol

NCT03430206

January 9, 2018

1) Name of study

Transnasal Humidified Rapid-Insufflation Ventilatory Exchange (THRIVE) Use in Pediatric Populations

2) PI and other key investigators or key study personnel

[name] – PD

[name] – COPD

[name] – other personnel

[name] - other personnel

[name] - other personnel

[name] – other personnel

[name] – other personnel

[name] - other personnel

3) Specific source of institutional funding (account number)

none

4) List of sources from whom you are seeking funds (or have sought funding) for this project

none

5) Specific aims and basic hypothesis including an explicit primary hypothesis or goal

Hypothesis: The application of THRIVE at 1-2L/kg/min up to 70L/min will reduce to incidence of desaturation events (defined by SpO₂ <90%) by 75%.

Secondary aims: to verify the safety of intraoperative use of THRIVE in pediatric populations in the operating room and assess the incidence of adverse effects.

6) General background (2 page maximum including published preclinical and animal data supporting basic hypothesis, if relevant)

The introduction of high-flow nasal cannula (HFNC) as Transnasal Humidified Rapid-Insufflation Ventilatory Exchange (THRIVE) to the operating theater has been demonstrated and validated in numerous studies in both adult and pediatric patients prior to intubation.^{1,2,3} It has including those undergoing laryngeal procedures and surgeries, to augment sedation-related hypoventilation, or as a substitute for apneic oxygenation, intermittent intubation or mask ventilation, or jet ventilation.^{4,5,6} Given the previously demonstrated safety and efficacy of high-flow nasal cannula in similar populations, we intend to study its use during relevant procedures.

7) Preliminary unpublished data (1 page maximum)

At Lucile Packard Children’s Hospital in 2017, a retrospective analysis of 3 months of eligible cases (pediatric patients undergoing microdirect laryngoscopy and bronchoscopy (MDLB) with or without other airway interventions in pediatric patients undergoing general anesthesia with a

natural airway) was performed and demonstrated that 54.5% (24/44) experienced at least one desaturation value below 90%, and 29.5% (13/44) experienced at least one desaturation below 80%. Given the incidence of desaturation events of 54.5% and serious desaturation events of 29.5%, it is clear that the current methods utilized to oxygenate patients undergoing these procedures may have the potential for improvement.

8) Experimental design and data analysis, including inclusion and exclusion criteria, statistical basis for the number of subjects to be enrolled, the statistical plan for analyzing at least the primary hypothesis, matrix showing procedure plan for each study visit, data safety monitoring plan (4 pages maximum)

We aim to enroll approximately 40 pediatric patients scheduled to undergo otolaryngologic or endoscopic surgeries or procedures under general anesthesia. At the time of enrollment, patients will be randomized to control or intervention arms using a random number generator.

The incidence of desaturation events <90% during microdirect laryngoscopy procedures under general anesthesia at our institution over the previous 3 months has been reviewed and found to be 54.5% of cases. Given an estimated reduction in desaturation events by approximately 75%, we will plan to enroll a total of 40 patients (20 in each arm) for a power of 80%.

Inclusion criteria: Pediatric patients <18yo undergoing general anesthesia for procedures or surgeries at Lucile Packard Children's Hospital.

Exclusion criteria: Pregnancy, absence of parent or legal guardian able to provide written consent for study participation, anatomical or surgical contraindications (epistaxis, basilar skull fractures or abnormalities, nasal surgery or obstruction, nasal fractures, nasal vascular abnormalities), congenital heart disease with admixture physiology, baseline oxygen saturation < 94%, emergent surgery for which application of HFNC might delay surgery or might result in increased aspiration risk.

9) Significance (1 paragraph or less)

With this study we hope to determine whether THRIVE is superior to current oxygenation and ventilation techniques utilized during general anesthesia without an advanced airway device, and determine whether the use of THRIVE can prevent adverse events such as oxygen desaturation and its sequelae. We also hope to verify the safety of the use of HFNC during general anesthesia in pediatric patients.

10) Key references

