# **Transnasal Humidified Rapid-Insufflation Ventilatory Exchange (THRIVE) Use in Pediatric Populations**

## **Statistical Analysis Plan**

**NCT03430206**

**July 9, 2020**

After IRB approval, patients were randomized to control or THRIVE. Controls received 100% oxygen via the side port of a Parson's laryngoscope to insufflate the oropharynx at 6-10 L/min, titrated by the anesthesiologist. THRIVE received 100% oxygen via HFNC at 2L/kg/min using an Optiflow machine. Inclusion criteria were all patients from birth to 18 years old. Exclusion criteria included papillomatosis, tracheostomy, or unrepaired heart disease.

The primary aim was surgical interruptions. A priori power calculation based on 15 pilot surgeries demonstrated the frequency of interruptions in the control to be 0.93 and 0.33 in THRIVE. Assuming a Poisson regression, 80% power, and 95% confidence interval, 27 patients in each group (54 total) were needed to demonstrate a significant difference. To account for incomplete data and dropouts, an additional 20 patients (74 total) were targeted for consent. The secondary aims were to compare differences in oxygen desaturation index (ODI), desaturations below 90%, transcutaneous carbon dioxide (tCO2), and adverse events.

Demographics and postoperative diagnoses in control and THRIVE were collected. Interruptions were defined as the need to pause surgery to provide airway support, such as mask ventilation or intermittent intubation. Pulse oximetry was recorded by second in the electronic medical record. ODI was defined as a 4% decrease in saturation from a 120 second rolling mean for greater than 10 seconds. TCO2 was recorded at procedure start and end. Adverse events (nausea, vomiting, sinus pain, throat pain, epistaxis) were recorded prior to discharge.

Outcomes were calculated using negative binomial regression with case duration as an offset in the unadjusted and adjusted models, with the exception of tCO2. Models were adjusted for postoperative diagnoses. As a result of interim analysis, it was determined that analysis of the outcome measure Absolute Incidence of Oxygen Desaturation Less than 90% would not provide statistically meaningful results when comparing the two groups, and this outcome was removed from the analysis plan.

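### With 20 to 27 THRIVE patients the trial can estimate adverse-event incidence but cannot verify safety, and the SAP's model for adverse events fails if an arm has none

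*Protocol*

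**What the plan says.** **Protocol, Section 5.** The secondary aim is "to verify the safety of intraoperative use of THRIVE in pediatric populations in the operating room", and the same sentence adds an assessment of how often adverse effects occur. It therefore has two parts, verifying safety and assessing incidence.

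**Protocol, Section 9.** The intention returns in softer form: "We also hope to verify the safety of the use of HFNC during general anesthesia in pediatric patients".

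**Protocol, Section 8.** The sample size comes from desaturation below 90%. The control incidence was "found to be 54.5% of cases", a reduction of about 75% is assumed, and "we will plan to enroll a total of 40 patients (20 in each arm) for a power of 80" percent.

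**SAP, second paragraph.** The sample size comes from surgical interruptions, with frequencies of 0.93 (control) and 0.33 (THRIVE): "27 patients in each group (54 total) were needed to demonstrate a significant difference". The consent target is 74, the extra 20 being an allowance for attrition and missing data. Adverse events are one of several secondary outcomes to be compared between arms.

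**SAP, third paragraph.** Five adverse events are named, with recording before discharge.

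**SAP, fourth paragraph.** "Outcomes were calculated using negative binomial regression with case duration as an offset in the unadjusted and adjusted models", tCO2 being the only exception given.

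Neither document states an acceptable risk, a safety margin, a precision target, or a method for sparse events.

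**The concern.** To verify safety is to show that risk lies below some tolerable level. That needs a stated level and enough patients to exclude risks above it. The plan has no such level, and safety played no part in either sample size. The only formal safety analysis is a between-arm comparison, and at this size a comparison that shows no difference carries little information.

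There is also a problem with the method. Adverse events are modelled in the same way as the count outcomes. For an uncommon event an arm may well have none, and the rate ratio then has no finite estimate. The SAP gives no fallback.

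At stake is how a secondary result about children is reported. A clean record in a small arm could be described more strongly than the data allow, or the planned analysis could fail to give a usable estimate.

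**Working it through.** **1. What the sample sizes were built for**

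*Protocol.* p1 = 0.545 and p2 = 0.545 × 0.25 = 0.136. Assume two-sided alpha 0.05 (the protocol states none), 80% power and no continuity correction:

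n = [1.96·√(2·p̄·(1−p̄)) + 0.842·√(p1(1−p1) + p2(1−p2))]² / (p1−p2)², with p̄ = 0.341

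This gives 19.9, so 20 per arm, which reproduces the protocol.

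*SAP.* For Poisson rates 0.93 and 0.33, two-sided 0.05 and 80% power, the rate-difference formula gives (1.96 + 0.842)² × (0.93 + 0.33) / (0.60)² = 27.5 per arm. Other standard variants give 25.2 to 30.0. The stated 27 is consistent with this.

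Neither calculation has a safety input.

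**2. What zero events would exclude**

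With no events in n patients, the exact upper 95% limit is 1 − 0.05^(1/n) one-sided and 1 − 0.025^(1/n) two-sided. The documents set no confidence level for safety, so 95% is assumed.

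| THRIVE patients with adverse-event data | One-sided | Two-sided |
|---|---|---|
| 20 (protocol) | 13.9% | 16.8% |
| 27 (SAP, evaluable) | 10.5% | 12.8% |
| 37 (half of 74, all with data) | 7.8% | 9.5% |

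The last row assumes equal allocation and no loss of adverse-event data.

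Conversely, the chance of seeing no event in 27 patients is (1 − p)^27. This is 44% at a true risk of 3%, 25% at 5% and 5.8% at 10%.

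**3. What the between-arm comparison could detect**

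Full binomial enumeration at 27 per arm, two-sided 5% level, with assumed risks:

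| Control vs THRIVE risk | Fisher exact | Uncorrected chi-square |
|---|---|---|
| 5% vs 15% | 7% | 23% |
| 5% vs 20% | 19% | 42% |

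**4. The model when an arm has no events**

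With log link, intercept a, log rate ratio b, durations tᵢ and dispersion k, an arm with no events contributes −(1/k)·Σ log(1 + k·tᵢ·e^(a+b)) to the log-likelihood. This keeps rising as b falls, so no finite b maximises it.

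A fit to simulated data (27 per arm, none in one arm, k fixed at 0.5) shows this. The profile log-likelihood is −13.14 at b = −2, −12.587 at −5, −12.5558 at −10 and −12.5556 at −20. The fitted b is −11.3 after 10 iterations, −21.3 after 20 and −31.3 after 30. Its standard error rises from 79 to 1.7 million.

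**5. How often an arm would have none**

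P(at least one arm has zero) = 1 − [1 − (1 − p)^27]², with the same risk p in both arms. For pooling, the exponent is 5 × 27 = 135, assuming five independent events of equal risk. The documents give no event rates, so all values of p are assumptions.

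| Risk per event | One event analysed | Five events pooled |
|---|---|---|
| 3% | 69% | 3.2% |
| 5% | 44% | 0.2% |
| 10% | 11% | below 0.1% |
| 20% | 0.5% | below 0.1% |

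**The case against.** Several points on the other side are sound.

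- **Assessing incidence is already an aim.** Section 5 says so in the same sentence, and Section 9 only hopes to verify. This stands: only the part about verifying safety needs to go.
- **The documents never treat non-significance as proof of safety.** A reader might infer that the plan will conclude safety from the absence of a significant difference. No passage says this, and the SAP speaks only of comparing differences. That inference is not supported.
- **A 10% risk is not out of reach on every reading.** A reader might take the figures to mean that 10% could never be excluded. The documents set no such benchmark. At 27 patients the one-sided limit is only just above it, and 37 patients with data and no events would exclude it on both conventions. The extra 20 consents are meant to cover losses, so 27 remains the planned evaluable number. But a patient with incomplete oximetry could still have adverse-event data.
- **The model does not fail outright.** What is lost is the finite point estimate and the Wald interval. Likelihood-ratio inference survives while the other arm has events. With 0 versus 4 events (Poisson, equal exposure), LR = 2 × 4 × ln 2 = 5.55, p = 0.019. The 95% profile upper limit for the rate ratio solves 8·ln(1 + θ) = 3.84, giving θ = 0.62. The SAP does not say that this approach would be used.
- **Pooling largely removes the empty-arm problem.** This is true (working, step 5), but the SAP does not say whether the five events are pooled or analysed singly.
- **The model is not assigned to adverse events by name.** Also true. It follows from a general sentence on outcomes that exempts only tCO2.

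**Conclusion.** The point holds in a limited form. Arms sized on efficacy can describe adverse-event incidence with wide limits; they cannot verify safety, for which the plan sets no criterion. Even a clean THRIVE arm would leave true risks up to 16.8% (n = 20) or 12.8% (n = 27) open at two-sided 95%, and 9.5% in the most favourable case of 37 patients with data.

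The modelling problem is conditional. It needs an arm with no events of the type analysed. That is plausible for an uncommon event analysed singly and unlikely for a pooled count. The probabilities rest on assumed risks, equal in both arms, and the pooled ones also on independence between events.

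The primary outcome and the sample size are untouched. This is a lower-severity point, worth considering because the remedy is cheap.

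**What to change.** 1. **Protocol, Sections 5 and 9.** Keep the aim of assessing the incidence of adverse effects and remove the words about verifying safety.
2. **SAP, fourth paragraph.** Exempt adverse events, as well as tCO2, from the negative binomial model. For each named event, and for any event if a pooled result is wanted, report the number and percentage of patients per arm with exact (Clopper-Pearson) 95% intervals, and a score or exact 95% interval for the risk difference.
3. **SAP, same place.** State the risk that zero events would leave open at the number actually evaluable, for example 12.8% at 27 patients, and that a non-significant difference will not be reported as verified safety.

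The cost is a few sentences and one simple table, with no extra patients or data collection. The downside is a more modest safety claim.

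### Age, a baseline variable spanning birth to 18 years, enters no analysis model; adding it to the adjusted models is a nearly free improvement

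*Protocol*

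**What the plan says.** **Allocation.** Protocol section 8 says that, when enrolled, "patients will be randomized to control or intervention arms using a random number generator". The SAP says only that "patients were randomized to control or THRIVE". Neither document mentions strata, blocks or a prepared list, and neither says that these were absent.

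**Sample size.** The Protocol states "we will plan to enroll a total of 40 patients (20 in each arm) for a power of 80" percent. The SAP, with surgical interruptions now primary, states that "27 patients in each group (54 total) were needed to demonstrate a significant difference". That figure rests on pilot surgeries that "demonstrated the frequency of interruptions in the control to be 0.93 and 0.33 in THRIVE", and 74 patients are targeted for consent to cover dropouts and incomplete data.

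**Population and data.** The SAP's first paragraph sets the age range as birth to 18 years. Its third paragraph says that "Demographics and postoperative diagnoses in control and THRIVE were collected". Age is not named, but it is ordinarily a demographic item.

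**Models.** The SAP's last paragraph specifies negative binomial regression, unadjusted and adjusted, with case duration as offset, for every outcome except transcutaneous carbon dioxide. Postoperative diagnosis is the only adjustment variable named.

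**The concern.** The age range is the widest that a pediatric trial can have, and the sample is small. If interruptions are more frequent at some ages, two things follow.

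- A chance difference in age between the arms moves the estimated rate ratio in that particular trial.
- Variation between patients that age could explain is left as overdispersion, which widens the confidence interval and lowers power below the figure obtained under the Poisson assumption.

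The planned adjustment does not clearly cover this. A postoperative diagnosis is settled after allocation. Age is fixed at baseline, and the SAP gives no reason for choosing the one and omitting the other.

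**Working it through.** **Inputs from the SAP.** Mean interruptions per case λ₁ = 0.93 (control) and λ₂ = 0.33 (THRIVE); 27 per group; 80% power; 95% confidence, taken as two-sided 0.05.

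**Inputs assumed.** Half of the patients are younger, and younger age multiplies the interruption rate by r = 1 (no effect), 2 or 3. The documents give no value of r.

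**1. The plan's own figure.** The rate-difference formula gives

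n = (1.960 + 0.842)² × (0.93 + 0.33) / (0.93 − 0.33)² = 27.5 per group.

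This rounds up to 28, against the stated 27, so the sample size reproduces closely. The log-rate Wald formula used in step 3 is more conservative and gives 75.7% power at 27 per group.

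**2. Overdispersion created by omitting age.** With rates in the ratio 1 : r, half of the patients in each group, the squared coefficient of variation is k = [(r − 1)/(r + 1)]².

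- r = 2: k = (1/3)² = 0.11
- r = 3: k = (2/4)² = 0.25

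**3. Approximate power with and without age.** Power = Φ( ln(0.93/0.33) / √[(1/0.93 + k)/27 + (1/0.33 + k)/27] − 1.96 ), where ln(0.93/0.33) = 1.036. With age in the model and no other overdispersion, k = 0.

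| r | k if age omitted | Power, age omitted | Power, age included |
|---|---|---|---|
| 1 | 0 | 75.7% | 75.7% |
| 2 | 0.11 | 73.5% | 75.7% |
| 3 | 0.25 | 70.8% | 75.7% |

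On this approximation the gain is 0, about 2 and about 5 points.

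**4. Simulation of the covariate alone.** These are negative binomial likelihood-ratio tests with 54 patients, simple allocation and no further dispersion. One run used 3,000 trials per cell (Monte Carlo standard error about 0.8 point). It gave 74% unadjusted against 78% age-adjusted for r = 3, and 77% against 80% for r = 2. A separate run put the gain at about 1 to 4 points for r = 2 or 3, and at 76% against 76% for r = 1. The range carried forward is 1 to 4 points, with no measurable penalty if age is irrelevant.

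In the first run, stratifying the allocation without adjusting gave no power gain (72% for r = 3, 76% for r = 2). The benefit comes from the model term.

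**5. Shift in the rate ratio from chance imbalance.** With about 27 per arm, the 95% limit on the difference in the proportion younger is 1.96 × √(0.5 × 0.5 × 2/27) = 0.267, for example 63.3% against 36.7%. The unadjusted ratio is then multiplied by [1 + (r − 1) × 0.633] / [1 + (r − 1) × 0.367].

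- r = 2: 1.633/1.367 = 1.20
- r = 3: 2.267/1.733 = 1.31

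About 1 trial in 20 would see a shift at least this large, in one direction or the other.

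**The case against.** The strongest reply is that nothing in either document shows age to be prognostic for interruptions. No age effect or age distribution is given, and age is not even named as collected. That is correct. The power gain is therefore conditional, and its size cannot be derived from the documents.

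A second reply is that the comparison above is with an unadjusted model, while the SAP also plans a diagnosis-adjusted one with a case-duration offset. If age acts partly through diagnosis or case length, some of its effect is already absorbed. That also stands, and the gain over the SAP's adjusted model may be smaller. A third is that chance imbalance is not bias and the confidence interval already allows for it. This is true, though adjustment can still sharpen the estimate.

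Stronger readings are tempting, and the documents do not support them.

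- *Allocation is unrestricted.* A reader might infer this from the mention of a random number generator, but such a generator can also produce a blocked list. The text shows only that no restriction is described.
- *Unequal arms undermine the sample size.* If allocation were simple, exactly 27/27 would occur with probability 10.8%. Averaged over the possible splits, however, power falls by only about 0.7 point at 54 patients and 1.0 point at 40. If all 74 consented patients were analysed, both arms would reach 27 with probability 98.6%.
- *The allocation must be blocked and stratified.* Simple randomization is valid. Short blocks within strata, in a single-hospital trial whose two treatments are visibly different, would make some assignments predictable.
- *Adjusting for postoperative diagnosis is itself biased.* Nothing in the documents shows that treatment affects the diagnosis. The point here is only that it is not a baseline substitute for age.

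**Conclusion.** The point holds as a low-cost improvement to the analysis, not as a demonstrated flaw. Age is in no model, and no stratification is described that would balance it across a birth-to-18-year range in about 54 patients. If younger age doubles or triples the interruption rate in half of the patients, the age term is worth about 1 to 4 points of power over an unadjusted model, and possibly less over the planned adjusted one. Under the same assumption it protects the rate ratio against chance shifts of about 1.2-fold to 1.3-fold at the 95% limit. If age has no effect, the cost is negligible. These sizes rest on the assumed age effect, on a half-and-half split, and on age entering the model in a form close to its true relation with the outcome.

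**What to change.** Rewrite the adjustment sentence in the SAP's last paragraph so that the adjusted models for interruptions and ODI include age as a prespecified baseline covariate, alongside whatever diagnosis terms are kept. State the form of the age term (continuous, or a two-level split) and give a brief reason for each covariate chosen.

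Keep age to a single term. At the planned rates only about 27 × 0.93 + 27 × 0.33 = 34 interruptions are expected, and the diagnosis categories, whose number is not stated, already draw on them. The cost is one degree of freedom, with no extra patients or procedures, provided that age was recorded with the demographics.

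The SAP is written in the past tense and mentions an interim analysis. If outcomes by arm have already been seen, report the age-adjusted result as an added, labelled analysis beside the planned ones. The sponsor should also describe how the allocation sequence was produced and concealed; changing it is optional.

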# **Transnasal Humidified Rapid-Insufflation Ventilatory Exchange (THRIVE) Use in Pediatric Populations**

## **Statistical Analysis Plan**

**NCT03430206**

**July 9, 2020**

After IRB approval, patients were randomized to control or THRIVE. Controls received 100% oxygen via the side port of a Parson's laryngoscope to insufflate the oropharynx at 6-10 L/min, titrated by the anesthesiologist. THRIVE received 100% oxygen via HFNC at 2L/kg/min using an Optiflow machine. Inclusion criteria were all patients from birth to 18 years old. Exclusion criteria included papillomatosis, tracheostomy, or unrepaired heart disease.

The primary aim was surgical interruptions. A priori power calculation based on 15 pilot surgeries demonstrated the frequency of interruptions in the control to be 0.93 and 0.33 in THRIVE. Assuming a Poisson regression, 80% power, and 95% confidence interval, 27 patients in each group (54 total) were needed to demonstrate a significant difference. To account for incomplete data and dropouts, an additional 20 patients (74 total) were targeted for consent. The secondary aims were to compare differences in oxygen desaturation index (ODI), desaturations below 90%, transcutaneous carbon dioxide (tCO2), and adverse events.

Demographics and postoperative diagnoses in control and THRIVE were collected. Interruptions were defined as the need to pause surgery to provide airway support, such as mask ventilation or intermittent intubation. Pulse oximetry was recorded by second in the electronic medical record. ODI was defined as a 4% decrease in saturation from a 120 second rolling mean for greater than 10 seconds. TCO2 was recorded at procedure start and end. Adverse events (nausea, vomiting, sinus pain, throat pain, epistaxis) were recorded prior to discharge.

Outcomes were calculated using negative binomial regression with case duration as an offset in the unadjusted and adjusted models, with the exception of tCO2. Models were adjusted for postoperative diagnoses. As a result of interim analysis, it was determined that analysis of the outcome measure Absolute Incidence of Oxygen Desaturation Less than 90% would not provide statistically meaningful results when comparing the two groups, and this outcome was removed from the analysis plan.

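### Child weight sets the flow contrast between the arms, from none at 3-5 kg to 7.0-11.7-fold at 35 kg, yet neither the randomisation nor any planned model uses weight

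*SAP*

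**What the plan says.** In the SAP's first paragraph, controls receive 100% oxygen through a laryngoscope side port "to insufflate the oropharynx at 6-10 L/min, titrated by the anesthesiologist. THRIVE received 100% oxygen via HFNC at 2L/kg/min". The SAP states no upper limit on the THRIVE flow. Protocol section 5 describes it differently: "The application of THRIVE at 1-2L/kg/min up to 70L/min".

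Eligibility covers the whole of childhood. The SAP states "Inclusion criteria were all patients from birth to 18 years old", and Protocol section 8 states "Inclusion criteria: Pediatric patients <18yo undergoing general anesthesia". Neither sets a weight limit or gives an expected weight distribution.

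On allocation, Protocol section 8 says that "patients will be randomized to control or intervention arms using a random number generator"; it mentions no stratification factor. On analysis, the SAP's last paragraph specifies negative binomial regression, offset by the length of the case, for every outcome except tCO2. The only adjustment named is this: "Models were adjusted for postoperative diagnoses". Demographics are collected, but weight is not named among them and they are given no role in the analysis.

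**The concern.** Both arms breathe 100% oxygen, so they differ in route and in flow. One flow is fixed as a range in L/min and the other is proportional to weight, so the flow part of the contrast changes with the child's size. In the smallest eligible children the set flows coincide or reverse; in the largest they differ many-fold. Weight, with age, may also affect how quickly a child desaturates, and so how often surgery is interrupted.

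A variable that both defines the size of the contrast and may predict the outcome is an obvious candidate for adjustment, and here it has no role. Three things are at stake: precision lost if weight is prognostic, chance imbalance left uncorrected in a small trial, and a single rate ratio whose value depends on which weights happened to be enrolled if the effect varies with the flow contrast.

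**Working it through.** **The plan's own figure.** The documents state no flow ratio. The nearest computed figure is the SAP's 27 per group, from 0.93 against 0.33 interruptions at 80% power. With two-sided alpha 0.05 (assumed), the rate-difference formula gives (1.960 + 0.842)² × (0.93 + 0.33) / (0.93 − 0.33)² = 7.849 × 1.26 / 0.36 = 27.5, so 28. The square-root version gives 25.8, so 26. The stated 27 is in line with these (a log-rate Wald version gives 30.0). The point does not depend on it, except as the trial size used below.

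**Where the flows meet.** THRIVE flow is 2 × weight. It equals the lowest control setting when 2w = 6, so w = 3 kg, and the highest when 2w = 10, so w = 5 kg. Below 3 kg it is lower than any control setting.

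**Set-flow ratio by weight.** The ratio is 2w/10 to 2w/6. The weights are assumed, since the documents give none.

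| Weight | THRIVE, L/min | Ratio to 10 L/min | Ratio to 6 L/min |
|---|---|---|---|
| 2.5 kg | 5 | 0.5 | 0.83 |
| 3 kg | 6 | 0.6 | 1.0 |
| 5 kg | 10 | 1.0 | 1.7 |
| 10 kg | 20 | 2.0 | 3.3 |
| 20 kg | 40 | 4.0 | 6.7 |
| 35 kg | 70 | 7.0 | 11.7 |
| 60 kg, Protocol ceiling | 70 | 7.0 | 11.7 |
| 60 kg, no ceiling | 120 | 12.0 | 20.0 |

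At the Protocol's lower figure of 1 L/kg/min, the flows meet at 6 to 10 kg, and the ratio at 35 kg is 35/10 = 3.5 to 35/6 = 5.8. The answer therefore depends on which description of THRIVE flow applies.

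**Chance imbalance.** With 27 per arm, the difference in mean weight, in SD units, has standard error √(2/27) = 0.272. The chance that it exceeds 0.25 SD in either direction is 2 × [1 − Φ(0.25/0.272)] = 2 × [1 − Φ(0.919)], about 36%.

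**What an arm-by-weight estimate could show.** This is a deliberately extreme simplification: two weight groups, Poisson counts, 27 per arm, a control rate of 0.93, a THRIVE rate of 0.33 in one group and no effect in the other. With 20% of patients in the no-effect group (5.4 and 21.6 per arm):
- no-effect group: variance of the log rate ratio = 2/(5.4 × 0.93) = 0.398
- other group: 1/(21.6 × 0.93) + 1/(21.6 × 0.33) = 0.190
- standard error of the difference = √0.588 = 0.767, and ln(0.33/0.93) = −1.036, so |z| = 1.35
- power = Φ(1.35 − 1.96), about 27%

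For shares from 20% to 50%, the power is about 27% to 34%. The no-effect group's own 95% interval is about 0.29 to 3.4 at a 20% share and 0.42 to 2.4 at 40%. A weight interaction can be estimated, but only imprecisely.

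**The case against.** The strongest defence is that the comparison is sound as it stands. Randomisation balances weight in expectation, and the confidence interval already allows for chance imbalance. Weight-scaled THRIVE against a comparator that the anesthesiologist titrates is a coherent pragmatic contrast, and its average effect is a legitimate target. All of this stands, and it rules out any claim of bias.

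Two stronger readings are tempting, and the documents support neither.

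First, a reader might infer that THRIVE can do nothing at 3-5 kg because the flows match. Equal set flow is not an equal intervention: one arm uses a laryngoscope side port and the other a humidified nasal cannula. The overlap in flow at the SAP's 2 L/kg/min also ends at 5 kg; by 10 kg the ratio is already 2.0-3.3.

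Second, a reader might take 0.93 and 0.33 as the rates in children who have a flow contrast, dilute them with no-effect children, and conclude that the trial is underpowered. Those are overall rates from 15 pilot surgeries with no weight split. If the pilot and trial had similar weight mixes, any dilution is already in the ratio 0.33/0.93 = 0.355. A 30% no-effect share would then require a rate ratio of (0.355 − 0.30)/0.70 = 0.08 in the rest, and a 40% share an impossible (0.355 − 0.40)/0.60 = −0.08. The documents do not show that the pilot mix differed from the trial's, so no loss of power can be derived.

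Timing is also a fair objection. The SAP is dated July 2020, is written in the past tense and reports an interim analysis, so full prespecification may no longer be possible.

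**Conclusion.** The point holds as a matter of precision and interpretation. At the SAP's 2 L/kg/min, the set-flow ratio runs from 0.6-1.0 at 3 kg to 7.0-11.7 at 35 kg. It stays there above 35 kg if the Protocol's 70 L/min ceiling applies, and reaches 12-20 at 60 kg if it does not. Neither document uses weight or age in stratification, adjustment or subgroups.

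The arithmetic is certain for set flow. That weight predicts interruptions, or that the THRIVE effect varies with weight, is plausible but not documented. The share of children at either extreme is unknown. The pooled rate ratio is valid as an average over whoever was enrolled; the plan does not describe it that way or provide a way to see how it varies. Conclusions for separate weight bands would not be supportable with 27 per arm.

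**What to change.** - Add baseline weight, on the log scale, as a covariate in the adjusted models for interruptions and ODI. Weight must be known to set a per-kg flow; the SAP should name it among the baseline variables.
- Report the weight distribution by arm.
- Give the THRIVE effect across continuous weight, from an arm-by-log-weight term with confidence intervals, as a supportive analysis of low power. No weight cut-point is needed.
- Label these additions post hoc if outcomes by arm have already been seen.
- State that the pooled rate ratio averages over the enrolled weight mix, and draw no conclusions for particular weight bands.
- Reconcile the THRIVE flow in Protocol section 5 (a range with a ceiling) with the SAP's first paragraph (a single figure, no ceiling stated). The ratios depend on it.

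The cost is SAP wording, one degree of freedom for each added term, and an interaction estimate that will be imprecise. No flow, procedure or patient number changes.
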